APPENDIX H

LIST OF EXCLUSIONARY DRUGS

This list of exclusionary drugs shall be reviewed and updated as needed and at least annually based on new information such as new marketed drugs. Citations are available upon request.

Amoxapine

Bupropion (at doses >300mg/day)

Clomipramine

Clozapine

Dantrolene

Disulfiram

Flumazenil

Ginkgo Biloba

Ginseng

Haloperidol

Illicit Drugs

Heroin

Ecstasy

LSD

Other illicit drugs

Isoniazid

Ketamine

Levodopa

Lidocaine and other local anesthetics

Loxapine

Maprotiline

Mefenamic acid (>1000mg)

Meperidine

Nelarabine

Olanzapine

Phenothiazines

Chlorpromazine

Fluphenazine

Perphenazine

Prochlorperazine

Promethazine

Thioridazine

Trifluoperazine

Piroxicam (> 20mg)

Stimulants

Amphetamine

Armodafinil

Benzphetamine

Cocaine

Dexmethylphenidate

Dextroamphetamine

Diethylpropion

Ephedra /Ephedrine containing herbal products

Lisdexamfetamine

Methylphenidate
Methamphetamine
Modafinil
Phendimetrazine
Phencyclidine (PCP)
Phentermine
Phenylpropanolamine
Pseudoephedrine
St John's Wort
Theophylline
Tiagabine
Tramadol
Vincristine

APPENDIX I

SEIZURE PROTOCOL AND FOLLOW-UP

Seizure Protocol and Follow-Up Procedures

Managing emergencies (syncope and seizures)

First: Stop the TMS session and remove the coil

Each TMS laboratory must institute an explicit plan for dealing with syncope and seizures, and every member of the TMS team must be familiar with it. There must be a place where the subject can lie down. All team members must be familiar with the means of summoning emergency medical help and when to call for it. Additionally, in laboratories performing rTMS at >1Hz, life-support equipment should be available.

Syncope usually is very brief. Seizures potentially induced by TMS, as well as seizures in general, are also brief (typically < 60 s) and without serious physical sequelae. Thus, efforts should be focused on preventing complications of the seizure or syncope rather than starting any specific medication, which is not required unless status epilepticus (which has been never described following rTMS) occurs. In most cases it is enough to lay the subject down. Supine position with the legs elevated is appropriate for suspected syncope. In case of seizures, attention must be taken to minimize the risk of aspiration and left lateral decubitus position is desirable. The description of additional medical emergency procedures to treat seizure complications go beyond the scope of the current guidelines.

Subjects who experience seizures with rTMS should be informed of the fact that they are not at a greater risk for further seizures than before. For some individuals, however, the potential psychological effects of having had a seizure can be significant and should not be ignored or minimized. Informed consent documents discuss the possibility of a seizure, and investigators must ensure that the subjects understand its implications. Both medical and psychological support must be provided to patients and normal subjects who have rTMS-induced seizures.

It is possible that the report of a seizure in a patient's medical record could be misinterpreted or used as a pretext for the denial of employment or medical insurance. Subjects of research studies should be informed of this possibility, and investigators must make certain that documentation of seizures is done in such a way that jeopardizes subjects to the minimum extent possible. Additional documentary support of a healthy subject's claim that a provoked seizure carries no adverse prognosis must be provided when appropriate.

Protocol for seizures

All personnel conducting TMS studies must be familiar with the Lab Policy for a seizure.

Responding to a seizure-

Sample protocol (UC Irvine protocol, courtesy, [name])

- If alone, call for help—
- If two people are present, the first stays with the subject and the second should go to get a nurse, who will call 911
- Immediately page MD if not physically present
- Remove harmful objects from the person's surrounding area
- If the person is in a chair, gently pull chair back away from metal instruments
- Loosen tight clothing from around the neck
- Cushion the head as much as possible
- Do NOT place fingers or any other objects in or near the person's mouth
- Do not attempt to hold the person down
- Remain calm, seizures almost always stop after a few minutes
- Observe what is happening, how long, etc—this can help the person later
- If a person is having trouble breathing, turn them on their side, provide oxygen mask
- After a seizure, stay with the person until paramedics arrive
- If there is concern for injury, do not move the person

Safety Equipment

Basic BLS supplies

Oxygen

Face masks

Crash cart-with medications readily available

Follow-up seizures

After a patient has been stabilized from a seizure during a TMS treatment, a neurologist will need to be contacted immediately, and the patient will be seen by a neurologist as soon as possible. Additionally, patients will have the following blood chemistries drawn as ordered by the MD.

Full metabolic screen (CBC, serum electrolytes including calcium and potassium)

Serum prolactin level, with the time noted when the serum was drawn relative to the seizure (that is, how many minutes or hours after the seizure was the sample drawn).

A urine sample should be collected and sent for a urine drug screen

The neurologist will likely schedule the patient for a brain scan (MRI or CT) and an EEG.

The above workup may provide an understanding of precipitating factors involved in the seizure, and whether follow-up care is needed.

If the workup is unrevealing, then it would be assumed that this was a TMS induced seizure with no sequelae, and a letter can be sent to the patient as in the Appendix.

If at any point during study participation, a participant has a seizure (not including syncope), that participant will be withdrawn from study treatments immediately (they will still be followed for protocol assessments). All seizures (not including syncope) will be considered serious adverse events and as such, will be reported using **Form 37 Adverse Event** in SharePoint and IRB **Form 119 Report of Serious Adverse Events and Unanticipated Problems** to the VA Central IRB using its website for the most-recent version:

<http://www.research.va.gov/vacentralirb/forms/investigator-forms.cfm>

What follows is a proposed letter to patient regarding seizure from the rTMS study.

Attachment: Letter to patients regarding seizure

Dear (patient's name)

On ____ (date) you experienced a seizure after you were given a study treatment of repeated transcranial magnetic stimulation (rTMS) as part of CSP #556, "The Effectiveness of rTMS in Depressed VA Patients". This letter is provided to explain the seizure occurrence to you and other health care providers.

Although seizures are rare when patients receive rTMS, they may occur. We assure you that this seizure probably occurred as result of the experimental treatment and does not indicate that you have any disease or other health or physical problem.

Please contact us at _____ if you have any further questions regarding this event.

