4. CLINICAL TRIAL DEVICES AND CLINICAL TRIAL AIDS

4.1 RTMS device and associated equipment. Following receipt of all required documentation (Section 2.1), the PCC will arrange for shipment, installation, and training of the rTMS device by the manufacturer.

4.2 Audiometer. Following receipt of all required documentation the PCC will ship one Earscan 3 screening audiometer to each site. Each audiometer includes a manual which is also available at <http://www.earscan.com/earscan3m.aspx>.

4.3 Alcohol and drug test kits. Following receipt of all required documentation and in anticipation of imminent randomization, PCC will ship commercially-available drug and alcohol tests to each site. These will be used in participants as specified in the protocol. These tests must be stored at room temperature in a locked room. Directions for use are included with each test. To reorder, sites should contact PCC via email, fax or phone.

4.4 Patient ID Cards – PCC will ship patient identification (ID) cards to each site. At the randomization visit, this wallet-sized ID card should be filled out and given to the subject with instructions to present the card to any clinician seen for medical treatment while participating in CSP #556. If additional Patient ID cards are needed, the site coordinator should contact PCC via email, fax or phone.

CSP 556 Patient ID card (Printing on Both Sides of the Card)

CSP #556 PATIENT IDENTIFICATION CARD
 
Patient's Name _____ Address _____ Phone # _____ Subject ID #: _____ Subject Treatment #: _____
 
I am participating in a clinical trial being conducted at the _____ During this trial I will have repetitive transcranial magnetic stimulation (rTMS) or sham treatment that may decrease my depression symptoms. Please contact the physician or nurse listed on the backside of this card if I require medical attention that might be affected by my participation in this trial or if you have questions regarding the trial.
	
IN CASE OF EMERGENCY, Please Notify:
 
Site Investigator: _____ Name _____ Work number _____ Nurse: _____ Name _____ Work number _____
 
National Clinical Trial Chairs: [name]. [contact] [name]. [contact] J. [name]. [contact] [name]
 
Pharmacy Coordinating Center: [contact] (24 hrs/7 days per week) Study Biostatistician: [contact] [name]
 
This card should be shown to any health care professional treating you for any reason.

---	---

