The MagPro R30 is an advanced high performance magnetic stimulator designed primarily for clinical use. The stimulator is often used for Transcranial Magnetic Stimulation (TMS) and repetitive Transcranial Magnetic Stimulation (rTMS) research.

With the repetition rate up to 30 pulses per second the MagPro R30 covers most protocol settings.

List of Core Specifications and Features

- Repetition Rate up to 30 pulses per second
- Pulse width 280 μ s with Biphasic Waveform
- Pulses in Train: 1-1000
- Number of Trains: 1-500
- Inter Train Interval: 1-120s

Treatment Chair

For optimal comfort a chair is part of the solution.
Possible to adjust seat height and tilting for best possible comfort.

Head rest for easy positioning of patient head during treatment.

Only 85 kg.

Airpump and Vacuum pillow

Airpump unit for vacuum pillows for easy support of patients head during magnetic stimulation.

The vacuum pillow consists of an airtight shell containing granules of polystyrene.

Super Flexible Arm

The flexible arm is used for easy positioning of the coil.

The arm has three joints. Two ball joints, of which two can rotate in multiple directions and one central joint can rotate in one direction. All three joints can be locked and unlocked by a single grip on the central handle. This allows a very flexible positioning of the coils.

Trolley

A Trolley is available to ease the mobility of the MagPro R30 stimulator.

For installations in countries with 100-120V mains, the 110V/230V Power Supply Option must be used.

Motor Threshold (MT)

As an important part of all research and clinical studies the Motor Threshold (MT) level for the patient must be determined.

To determine the motor threshold the C-B60 Coil is used for stimulating the motor cortex and the MEP Monitor for measurement of the resulting Motor Evoked Potential.

C-B60 Coil

Before performing the research study with the Cool-B65-A/P Coil the motor threshold for each patient must be found.

For this purpose the C-B60 Coil can be used. The magnetic field from this coil is equal to the active side of the Cool-B65-A/P Coil.

Built-in amplitude controls on the coil handle. This together with the small weight makes it very flexible and easy to operate with one hand.

[figure not shown]
[figure not shown]
- Max initial dB/dt: 32 kT/s near the coil surface
- Active pulse width: 280 μ s (Biphasic)

MEP Monitor

[figure not shown]

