- Max initial dB/dt: 32 kT/s near the coil surface on the active side, same as Cool-B65 Coil.
- The magnetic field near the coil surface on the placebo side is <5% of active side
- Active pulse width: 280µs (Biphasic)
- Protocol: 2pps Setup: Output=100%:
Number of stimulations before warm-up: > 20,000 pulses
- Typical Protocol: 60 trains @ 50 pulses/train @ 10pps @ Inter Train Interval: 25s @ Output=120% of MT.
Performance: Number of stimulations before warm-up: > 10,000 pulses (i.e. more than 3 patients on a row).
- Larger ergonomic handle
- All cables and cooling tubes combined in one cable

Lifetime

Due to mechanical, magnetically and thermal stress on the coil-winding inside the Cool-B65-A/P Coil, the lifetime of the coil is limited.

The lifetime is defined as maximum 5 years or Equivalent Pulse Value (EPV) of maximum 18.000.000 stimulations whichever occurs first.

When the coil reach the limit it will stop working and it has to be replaced with a new coil. The coil is handled as "electronic waste" and is not serviceable when it has reached the limit.

The EPV value is dependent on stimulation current waveform and amplitude. See example below.

Running a protocol of 3000 pulses at 75% MagPro indicated output power, using standard biphasic pulses:

The EPV is 4, and the 3000 pulses is equivalent to 12.000 EPV's. Providing a lifetime of 4.500.000 stimuli corresponding to 1.500 run of the protocol !

Benefits with Cool-B65-A/P for placebo studies

- It is possible with same coil to perform active stimulation and placebo stimulation
- No change in mechanical design and weight from side to side
- No change in sound level during stimulation in active and placebo mode
- Heating up of the coil is the same in active and placebo mode
- No labeling on the coil telling which is active side and which is placebo side
- Output current stimulator for surface electrodes on the patient for sensory sham

External Cooler Unit

- The Cool-B65-A/P is connected to an external Cooler Unit for circulation of liquid fluid as cooling media.
- Low noise system with very high performance.

Sham Noise Generator

[figure not shown]
The sound level from the coil during active stimulation and placebo is the same. But to sham the noise during the operation 100%, both patient and operator are connected to the Sham Noise Generator.

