The magnetic field originating from the stimulation coil stimulates a mild skin sensation when passing from the coil winding in to the brain. When using sham stimulation this effect is not present: To blind the patient to the sensation, a current stimulator is build in to the handle of the A/P-coil, and surface electrodes are placed just below the stimulation coil. For every magnetic stimulus a synchronous current stimulus is provided inducing an equivalent skin sensation. The current stimulator should be used both when using sham and active stimuli to insure blinding of the operator.

“Blinding” of the Operator....

[figure not shown]
We encourage the use of the multifunctional liquid cooled A/P coil. As described above, the A/P coil provides Active or Placebo stimulation, depending on which side is turned up/down. The coil winding is placed near one side and turning this side against the patient induces active stimulation. In the opposing end of the coil housing a shielding system is integrated to attenuate the field and also to balance the weight of the coil. When the coil is flipped 180 degrees, the distance from the coil winding to the patients head is much increased. The resulting remaining magnetic field is attenuated by the shield, and less than 10% of the active field is left in the Sham position.

The encapsulation of the A/P-coil is completely symmetrical, with no markers revealing which side is active and which is sham.

The A/P coil is equipped with a small orientation-sensing device. This device reports to MagPro which side of the coil is turned towards the patient, and in this way MagPro can detect if active or sham treatment is taking place.

It is not possible to start the treatment before the correct coil is inserted and the correct side is turned towards the patient. The MagPro will display the messages “Incorrect Coil” and “Flip Coil” if the actual setup does not match the specified setup stored.

When the coil is in-place, the MagPro is enabled and the amplitude adjusted to the agreed amplitude. Pressing the Start button will initialize the full sequence. When the treatment is ended successfully (or interrupted for some reason), a line with treatment information is stored.

[figure not shown]
[figure not shown]
Controlling studies

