To determine the necessary level of power that must be used, the establishment of a “motor threshold” (MT) is the most commonly employed technique (Kiers et al. 1993; Pridmore et al. 1998). The MT is usually defined as the minimum amount of electricity needed to produce movement in the contralateral thumb, when the coil is placed in the appropriate spot over the primary motor cortex (Pascual-Leone et al. 1993). The MT determining method has been improved with the use of an electromyograph (EMG) that is easier to teach, train, and operationalize than the visual method. In the recently completed NIH TMS trial, 3 of 4 sites used the EMG method, while one site used visual movement. The TMS vendor has incorporated a sophisticated EMG system within the TMS device and will provide the necessary software. A procedure called Maximum-Likelihood Strategy using Parameter Estimation by Sequential Testing MLS-PEST is a mathematical algorithm that is a promising alternative to traditional, time-consuming methods for determining MT. Because the EMG-PEST method is totally automated, it may prove useful in studies using MT as a quickly changing variable, as well as in large-scale clinical trials (Mishory et al. 2004). [name] Stimulation Lab has developed simple algorithms to use with the EMG system that can make MT determination rather rapid (8 pulses) and highly reproducible, essentially reducing and eliminating operator error, and almost like an automatic blood pressure cuff.

MT will be determined using Motor Evoked Potential (MEP) and the Parametric Estimation by Sequential Testing (PEST) procedure along with the CB60 coil. Refer to the MEP Monitor Use Guide in Appendix G Device Information.

3. *Treatment Administration*

Treatment will be administered following these procedures:

- A qualified registered nurse, nurse practitioner, or physician assistant will administer the treatment as well as determine all MT's, except for the one done at screening.
- The treatment administrator and all study personnel will be masked to the treatment.
- All treatments will be conducted in a business-like manner minimizing personal contact with the patient.
- The Cool-B65 A/P coil is used for treatments.
- The treatment location will be 6 cm anterior (i.e., forward) to the hand motor area stimulation point identified above, on a para-sagittal line, using the marking cap procedure.

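### The seizure letter attributes the event to rTMS and rules out disease, although the participant may have been on sham and the sender is masked

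*Protocol*

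**What the plan says.** Appendix I, under follow-up of seizures, sends the participant to a neurologist and lists blood tests, a serum prolactin, a urine drug screen and a likely brain scan and EEG. It then gives a default: "If the workup is unrevealing, then it would be assumed that this was a TMS induced seizure with no sequelae". On that footing the attached letter may go out.

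The letter is addressed to the participant and is also meant to explain the event to other health care providers. It states that the seizure followed rTMS given as study treatment, and then: "We assure you that this seizure probably occurred as result of the experimental treatment and does not indicate that you have any disease". The sentence goes on to exclude other health or physical problems too.

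Other parts of the protocol describe exposure differently:

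- Section 4.4 (Patient ID Cards) puts on the card shown to outside clinicians: "During this trial I will have repetitive transcranial magnetic stimulation (rTMS) or sham treatment that may decrease my depression symptoms".
- Appendix K, section 3 (Treatment Administration): "The treatment administrator and all study personnel will be masked to the treatment". Section 8 (Masking) extends the mask to the patient.
- Appendix G (device information) gives the sham-side field twice: "The magnetic field near the coil surface on the placebo side is <5% of active side" and "less than 10% of the active field is left in the Sham position".

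After a seizure the participant stops study treatment but stays in protocol assessments (Appendix I).

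**The concern.** The trial is sham-controlled, and whoever sends the letter under the stated rule does not know the arm. A negative workup does not reveal it. For an active recipient, attributing the seizure to rTMS is a reasonable default. For a sham recipient, the same negative workup means an unexplained seizure, and the letter presents it as a provoked one.

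What is at stake is mainly patient safety. A sham recipient with a first seizure, and any clinician who later reads the letter, would have written assurance that the study treatment probably explains it and that no disease is indicated. That could discourage further evaluation in the cases where no cause has been found. The participant would also hold two study documents that disagree, since the ID card allows for sham and the letter does not.

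A minor second effect is on the mask. The letter implies active treatment to someone who is still being assessed and who will later be asked to guess the assignment.

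**Working it through.** The protocol gives no figure to reproduce here. The check sets the statements in the letter against what a sham recipient actually receives.

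**Statement by statement, for a sham recipient**

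| Letter | Elsewhere in the protocol | Result |
|---|---|---|
| rTMS was given | ID card: rTMS or sham; sham uses the placebo side of the coil (Appendix K, section 7) | False |
| It probably caused the seizure | Sham field under 5% or under 10% of active | Not supported |
| No disease is indicated | Rests on a negative workup plus the assumed TMS cause | Only the workup remains |

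**Residual field on sham.** Treatment is set at 120% of motor threshold. If the field scales with output, the sham side gives less than 0.05 × 120% = 6%, or less than 0.10 × 120% = 12%, of the threshold intensity. Low-current scalp stimulation is added to mimic the sensation (Appendix K, section 8).

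**Real-coil exposure on sham.** Sham recipients do receive genuine pulses during motor-threshold (MT) determination with the C-B60 coil. Appendix G says of it: "The magnetic field from this coil is equal to the active side of the Cool-B65-A/P Coil".

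Inputs, all from Appendix K:

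- Determinations: 1 at screening, 1 per five-session block (the first block's being that of the first treatment day), and 1 per taper block, taken here as three weekly blocks for remitters only.
- Pulses per determination: 8, from the remark that the algorithms "can make MT determination rather rapid (8 pulses) and highly reproducible".
- Treatment pulses on active: 4,000 per session, 20 to 30 sessions, plus 3 + 2 + 1 = 6 taper sessions where they apply.

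Ratio = (determinations × pulses per determination) ÷ (sessions × 4,000).

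| Course | Determinations | MT pulses at 8 each | Treatment pulses on active | Ratio | Ratio at 50 each (assumed) |
|---|---|---|---|---|---|
| 20 sessions | 1 + 4 = 5 | 40 | 80,000 | 0.050% | 250 / 80,000 = 0.31% |
| 20 + taper | 5 + 3 = 8 | 64 | 104,000 | 0.062% | 400 / 104,000 = 0.38% |
| 30 sessions | 1 + 6 = 7 | 56 | 120,000 | 0.047% | 350 / 120,000 = 0.29% |
| 30 + taper | 7 + 3 = 10 | 80 | 144,000 | 0.056% | 500 / 144,000 = 0.35% |

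The protocol does not fix the number of pulses per determination, so 50 is an assumed upper value. Even then the ratio stays below 0.4%.

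**The case against.** The strongest reply is that the letter is a proposed, optional template whose causal sentence is hedged. It follows a full neurological workup, which gives the no-disease sentence some support in either arm. Every seizure is also reported as a serious adverse event, and the adverse event form asks separately about attribution to device, treatment, medication and other patient conditions. Harm needs several uncommon things together: a sham recipient, a seizure during a session, a negative workup, and the letter sent unedited with the arm unchecked. Appendix G puts seizure risk with rTMS below 1%, and no sham-arm rate is given. All of this stands, and it limits the weight of the point.

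Three further objections stand in part:

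- **Unmasking rules.** The main text of the protocol, which is not covered here, may contain an unmasking procedure; the deviation form's code for inappropriate unblinding hints at one. Appendix I does not make the letter depend on it. Nor does it name who makes the causal assumption, but under Appendix K all study personnel are masked.
- **Pulse counts.** A ratio of pulses is not a ratio of seizure risks. The table shows only how little real stimulation a sham recipient gets.
- **Employment and insurance.** Appendix I wants participants protected against misuse of a seizure record, and a neutral letter protects active recipients less. That is a real cost, but it lasts only until the assignment is confirmed.

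None of these gives a reading under which the stated rule produces a correct letter for a sham recipient.

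**Conclusion.** The concern holds. As written, the rule in Appendix I can send a sham recipient and their clinicians a letter that is wrong about exposure and unsupported on cause. Its no-disease assurance would then rest on a negative workup alone.

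The event is rare, with seizure risk on rTMS below 1% and presumably lower on sham. The likelihood of a wrong letter cannot be calculated from the document. The real-coil exposure of a sham recipient is about 0.05% to 0.06% of an active course by pulse count, and under 0.4% at the assumed 50 pulses per determination.

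This rests on three assumptions: three weekly taper blocks, 8 pulses per determination as the base value, and no rule in the main text that ties the letter to a confirmed assignment. No estimate, endpoint or stopping rule is affected. The wording should be corrected because it is a participant-facing safety document and the correction is easy.

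**What to change.** 1. In Appendix I, follow-up of seizures, delete the default assumption of a TMS-induced seizure without sequelae. State instead that the cause is not established while the assignment is masked.
2. Reword the letter to match the ID card: the participant received either active or sham stimulation, the cause of the seizure has not been established, and further evaluation should be discussed with the neurologist.
3. Allow a causal or no-disease statement only after the party holding the codes has confirmed active assignment and the neurologist agrees.

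The workup, serious adverse event reporting and withdrawal from study treatment stay as they are.

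The cost is one clause, one template and IRB review of the letter. The downside is that a causal letter for employment or insurance purposes is delayed until the assignment is confirmed, which means unmasking that one case.
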